8.3 Sample Size

Because the efficacy of this treatment is almost completely unknown, we would like to reject the treatment as quickly as possible with a small number of subjects if the treatment is not effective.

A response probability of 30% or less would warrant terminating the treatment on this subject population, and we hypothesize that the actual response probability using this treatment would reach 50% or more.

Let p be the probability of complete or partial response at 3 months. Our sample size is determined by testing the null hypothesis $H_0: p \leq 30\%$ versus the alternative $H_1: p \geq 50\%$ at 0.05 significance level and 0.80 of the power. We determine the sample size using the Two-Stage Minimax Design outlined in Table 1 of Simon (1989)⁷⁵ This design is selected because it requires a smaller total number of subjects ($n=39$) than the Simon's Two-Stage Optimal Design ($n=46$). At the first stage, 19 subjects will be accrued and the null hypothesis will be accepted (i.e., the treatment will be terminated) if 6 or less subjects respond to the treatment at 3 months. If 7 or more subjects respond to the treatment at 3 months in the first stage, then an additional 20 subjects will be accrued, bringing the total number of subjects to $n=39$. The null hypothesis of $p \leq 30\%$ will be accepted if the total number of complete and partial responders at 3 months is 16 or less.

An additional 39 subjects will be enrolled to allow for statistically valid subgroup comparisons of secondary endpoints such as response to cyclosporine in subjects who relapse within six months of treatment.

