2.4.1 Clinical evidence of immune mechanisms

- Twenty-one of sixty-one patients (33%) with MDS treated at the NIH with h-ATG immunosuppression (protocol 95-H-0189) became transfusion-independent.
- Three of 18 patients (17%) with MDS treated with CsA immunosuppression (96-H-0142, 99-CC-0021) became transfusion independent
- In a separate report, two patients with hypoplastic MDS responded to h-ATG and CsA either alone or in combination with durable responses. ¹
- In various other case reports, 8 of 13 patients with hypoplastic MDS have responded to h-ATG treatment ^{2,3}
- h-ATG treatment improved the cytopenia of MDS that had evolved from aplastic anemia. ⁴
- In 17 cytopenic patients with MDS of the refractory anemia subtype, 82% responded to treatment with CsA alone ⁵.
- Four patients with autoimmune diseases and myelodysplasia showed hematological responses to CsA. ⁶
- In 30 patients with autoimmune diseases and MDS, 6 showed a hematological response to steroid treatment including one complete cytogenetic response. ⁷
- CsA induced a remission in an infant with myelodysplastic syndrome ⁸
- Our experience with 133 patients treated over a 10 year period with ATG or ATG/CsA demonstrating response rates of over 70% in patients in high or intermediate risk groups (see section 2.4)

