2.10 Scientific and Clinical Justification of the Protocol

Selected MDS patients generally respond very well to h-ATG or CsA. However, there is substantial morbidity associated with h-ATG administration in this group of patients. In a previous trial using h-ATG/CsA to treat MDS, 7/38 patients died within a three month period of time following treatment; three deaths were directly attributable to h-ATG. In addition, 6/38 had a life threatening toxicity directly attributable to the h-ATG.

Our initial experience with alemtuzumab (Campath®) in severe aplastic anemia as salvage treatment for patients who have failed a first course of h-ATG have been encouraging. Infusion-related toxicities have been modest and immunosuppression-related toxicities, including infections, compare favorably to what is observed with h-ATG or r-ATG. In our preliminary experience of 12 patients, hematologic response rates have been as at least equivalent to r-ATG. Should alemtuzumab (Campath®) produce comparable responses to h-ATG but without the toxicity, alemtuzumab (Campath®) would be an attractive treatment, particularly in this group of patients who have substantial co-morbidities.

[figure not shown]
In our previous experience treating 133 patients with MDS with immunosuppression, we demonstrated the superiority of combination ATG and CsA over either drug alone ($p=0.02$) (unpublished data). Furthermore, we noted that many patients relapsed following discontinuation of CsA, and required long-term continuation of the medication to maintain normal counts. Campath-1H is more immunosuppressive than ATG, but we are concerned about potential for relapse in the months after the effects of Campath-1H wane. Therefore we will allow institution of CsA in patients responding to Campath-1H but relapsing 3 months after initial response to Campath-1H measured at 3 months. As the half-life of Campath-1H is 12 days this would minimize the potential for increased toxicity. We will collect data on relapse rates and recovery of relapsing patients after institution of CsA.

We will treat patients who relapsed following Campath-1H with CsA regardless of prior response to CsA treatment. In patients who did not respond to CsA prior to Campath-1H, it is possible that CsA may have activity in the post Campath-1H setting due to a Campath-related alteration of the underlying disease.

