4.2 Exclusion Criteria

- 4.2.1 Chronic myelomonocytic leukemia (CMML) , WHO RAEB-2 (see section 2.2)
- 4.2.2 Secondary MDS
- 4.2.3 Failure to respond to prior therapy with ATG or ATG/CsA
- 4.2.4 Prior therapy with combination chemotherapy
- 4.2.5 Transformation to acute leukemia (FAB sub-group RAEB-T, i.e., greater than 20% blasts in marrow aspirate)
- 4.2.6 Failure to discontinue the herbal supplements *Echinacea purpurea* or *Usnea barbata* (*Old Man's Beard*) within 2 weeks of enrollment
- 4.2.7 Active infection not adequately responding to appropriate therapy
- 4.2.8 HIV positive patients
- 4.2.9 Active malignant disease (excluding non-melanoma skin carcinoma)
- 4.2.10 Moribund status or concurrent hepatic, renal, cardiac, neurologic, pulmonary, infectious, or metabolic disease of such severity that it would preclude the patient's ability to tolerate protocol therapy or that death within 7-10 days is likely
- 4.2.11 Life expectancy less than 6 months
- 4.2.12 Low predicted probability of response (see section 2. 2)
- 4.2.13 Previous hypersensitivity to alemtuzumab (Campath®) or its components
- 4.2.14 Current pregnancy, or unwilling to take oral contraceptives or refrain from pregnancy if of childbearing potential
- 4.2.15 Not able to understand the investigational nature of the study or give informed consent

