8.2 Secondary Endpoints

8.2.1 Transfusion-independence for red blood cells and/or platelets: ability to maintain a hemoglobin >8gm/dl and a platelet count > 20 000/ μ L without the need for transfusions for a period of 6 weeks regardless of subsequent events.

8.2.2 Overall survival which is defined as the time elapsed between time of treatment and death and will be compared between responders and non-responders. Any such comparison may be biased and needs to be interpreted cautiously.

8.2.3 Life threatening toxicity. Subjects who do not complete the treatment course because of toxicity or voluntary withdrawal will be included in analyses.

8.2.4 Overall survival and transformation-free survival, which is defined as the time elapsed (reported at 3 month intervals for the first four years, then yearly thereafter) between time of treatment, and bone marrow morphologic evidence for progression (as determined by FAB criteria), development of acute leukemia, or death will be compared between responders and non-responders. Any such comparison may be biased and needs to be interpreted cautiously.

8.2.5 Response duration will be determined as the interval between time of onset of response as outlined above, and the time of relapse or loss of response characteristic (reported at 3 month intervals for the first four years, then yearly thereafter).

8.2.6 Affects of the addition of cyclosporine. Subjects who relapse after responding to Campath will be given CsA to determine if CsA will be beneficial under these circumstances. For this protocol, CsA is investigational, subjects will be followed, data will be collected and analyzed as secondary endpoints. The number of subjects who will receive CsA cannot be predicted since it will depend on the initial response to Campath which is unknown.

Response proportion, response duration, overall survival, and transformation free survival will be determined and compared within the FAB sub-groups and International Prognostic Scoring System categories of MDS and with the results of previous studies at the NIH using h-ATG alone or CsA alone to treat the cytopenia of MDS.

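### Rejecting a 30% response rate shows activity only, and the planned historical comparison omits the h-ATG+CsA cohort and any restriction by prediction score, so the comparability rationale of section 2.10 goes untested

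*Combined protocol and SAP*

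**What the plan says.** **Population.** Section 3.0 selects subjects with the section 2.2 prediction model, and 4.2.12 excludes those with a low score. High and intermediate scorers remain.

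**Existing treatment in those score groups.** Section 2.4.1 describes 133 patients given ATG or ATG/CsA, "demonstrating response rates of over 70% in patients in high or intermediate risk groups". Table 2 in section 2.2 shows 8 of 9 high scorers and 0 of 2 intermediate scorers responding. Section 2.5.7 gives 90% for high scorers on h-ATG+CsA.

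**Rationale.** Section 2.10 would find the drug attractive should it "produce comparable responses to h-ATG but without the toxicity". The toxicity evidence there is from the combination: "In a previous trial using h-ATG/CsA to treat MDS, 7/38 patients died within a three month period of time following treatment". It attributes three of those deaths, and life-threatening toxicity in a further 6/38, directly to h-ATG.

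**Success rule.** Section 8.3 states "A response probability of 30% or less would warrant terminating the treatment on this subject population". The alternative is a rate of at least 50%. The section uses a Simon minimax design "at 0.05 significance level and 0.80 of the power": stop at 6 or fewer of 19, and accept the null at 16 or fewer of 39. A further 39 subjects are added for secondary comparisons, making 78. No source is given for the 30%.

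**Historical comparison.** Section 8.2 compares response, its duration and survival within FAB and IPSS categories and "with the results of previous studies at the NIH using h-ATG alone or CsA alone to treat the cytopenia of MDS". It gives no score restriction and no h-ATG+CsA cohort.

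**The concern.** The question that motivates the trial is comparative: does alemtuzumab give responses like those to h-ATG at a lower cost in toxicity? Two parts of the plan could speak to it, and neither does so as written.

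The success rule tests against 30% in a group for which the protocol itself reports over 70% on existing immunosuppression. A trial that performs exactly as hypothesised, at 50%, would be called positive at a rate 20 points below that figure, and nothing in section 8 says how the result should then be described.

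The historical comparison sets a cohort enriched for likely responders beside single-agent series with no stated score restriction, which tends to flatter the new treatment. It also leaves out the combination, which supplies the toxicity figures in 2.10 and which 2.10 calls superior to either drug alone. The toxicity half of the argument therefore rests on one cohort and the response half on others.

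**Working it through.** **1. Reproduce the plan's design.** With X ~ Bin(19, p) in stage 1 and Y ~ Bin(20, p) in stage 2,

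P(success | p) = Σ from x = 7 to 19 of P(X = x) · P(Y ≥ 17 − x).

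| True response | P(success) |
|---|---|
| 30% | 0.0455 |
| 40% | 0.356 |
| 45% | 0.599 |
| 50% | 0.804 |
| 70% | above 0.999 |

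A full search at p0 = 0.30, p1 = 0.50, one-sided 0.05 and 80% power returns 6/19 and 16/39 as the minimax design, and n = 46 for the optimal design. Both agree with section 8.3, so the arithmetic is right.

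**2. What a pass looks like.** Exact (Clopper-Pearson) 95% intervals, ignoring the stage 1 look:

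| Result | Rate | 95% CI |
|---|---|---|
| 17/39 (smallest success) | 43.6% | 27.8% to 60.4% |
| 21/39 | 53.8% | 37.2% to 69.9% |
| 22/39 | 56.4% | 39.6% to 72.2% |
| 28/39 | 71.8% | 55.1% to 85.0% |

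Results from 17 to 21 of 39 pass with an upper limit below 70%. A result such as 28/39 would be informative about comparability, but the pass itself would not be what showed it.

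**3. How firm the 70% is.** The only score-group counts shown are in Table 2: (8 + 0)/(9 + 2) = 8/11 = 72.7%, exact CI 39% to 94%. The text below that table gives 7 of 8 for high scorers, which would make it 7/10 = 70%. Section 2.4.1 gives no group size, response definition or assessment time for its figure.

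**4. Why a fixed 70% must not be the yardstick.** Suppose 39 of 78 respond. The exact interval is 38.5% to 61.5%, which excludes 70%. Now let the benchmark carry its own error, using 8/11 for illustration and the Newcombe interval built from Wilson limits (39/78: 0.392 to 0.608; 8/11: 0.434 to 0.903):

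- difference = 0.500 − 0.727 = −0.227
- lower = −0.227 − √[(0.500 − 0.392)² + (0.903 − 0.727)²] = −0.43
- upper = −0.227 + √[(0.608 − 0.500)² + (0.727 − 0.434)²] = +0.09

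The interval includes zero (Fisher p = 0.21). Under a fixed-70% rule with 78 subjects, every result up to 46/78 (59.0%, upper limit just under 70%) would be labelled lower response.

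**5. The comparators side by side.**

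| Regimen | Role in 2.10 | In the 8.2 comparison? |
|---|---|---|
| h-ATG alone | named response comparator | yes, no score restriction stated |
| CsA alone | none as a comparator | yes, no score restriction stated |
| h-ATG+CsA | source of 7/38 deaths and 6/38 life-threatening toxicities; called superior | no |

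As a guide to what an unrestricted series looks like, the h-ATG series in 2.4.1 is 21/61 = 34.4% (printed as 33%), counted as transfusion independence.

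**6. An unresolved contradiction.** Section 2.10 reports the combination as better than either drug alone (p = 0.02). Section 2.5.7 reports a p = 0.02 contrast in high scorers that favours h-ATG regimens over CsA + h-ATG. The two passages must be reconciled.

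**The case against.** This is a pilot Phase I/II trial of a drug whose efficacy section 8.3 calls almost wholly unknown, and its stated aim is to drop an ineffective treatment quickly. A 30%/50% Simon design passing 80% of the time at 50% is what such a design is built to do. No passage says that rejecting 30% establishes equivalence to ATG, and the sentence in 2.10 is conditional. All of this stands, and it is why the two-stage rule should be left alone.

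h-ATG alone, the comparator that 2.10 names, is already in 8.2. The harms in the combination trial are also attributed in part to h-ATG itself, which narrows the mismatch between the toxicity and response references. Response proportions with 95% intervals (8.4) and life-threatening toxicity (8.2.3) are already planned. These points stand too. What remains is the missing cohort, the missing score restriction and the missing statement of what a pass means.

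Stronger readings are tempting, and the documents do not support them:

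- **The 30% was carried over from the 21/61 h-ATG series and never adjusted for enrichment.** Section 8.3 gives no source. The figures differ (30% against 34.4%), and so do the outcomes: transfusion independence there, and complete or partial response, including a single minor response, here.
- **A result whose upper limit falls below 70% shows lower response than existing immunosuppression.** Steps 3 and 4 show why not.
- **The benchmark describes the same patients.** This trial admits prior responders to h-ATG or h-ATG/CsA and uses WHO classes without RAEB-2, whereas the series in 2.5.7 used FAB RA, RARS or RAEB. Timing also matters: response is scored at 3 months here, and mean time to response on h-ATG alone was 3 months.

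**Conclusion.** The concern holds in a limited form. The two-stage design is correctly calculated and is a reasonable activity screen. Passing it, possible at 17/39 (43.6%) and 80% likely at a true 50%, says nothing about comparability with immunosuppression that the protocol credits with over 70% in the same score groups. The comparison that could address this is stated without a score restriction and without the h-ATG+CsA cohort.

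The conclusion does not depend on 70% being exact. It needs only that response in high and intermediate scorers is plausibly well above 30%, as every score-group figure in the protocol for h-ATG or h-ATG+CsA suggests. It assumes that the institute holds patient-level scores and outcomes for both cohorts. Section 2.5.7 confirms in-house combination patients (31) and scores for 95 patients across the regimens, but 2.10 does not say outright that its 38-patient trial is the institute's own. It would be wrong to conclude that the trial is invalid, that 30% is the wrong null, or that alemtuzumab would be inferior at any given rate below 70%.

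**What to change.** Keep the two-stage design and the sample size.

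1. **8.3:** state that rejecting 30% shows activity only and is not evidence of response comparable to h-ATG.
2. **8.2:** name the in-house h-ATG+CsA cohort as a comparator beside h-ATG alone, and identify which series it is. Restrict both cohorts to high and intermediate scorers, and apply this trial's 3-month response definition where the data allow.
3. **8.2:** compare both response and early death or life-threatening toxicity against those same cohorts.
4. **8.4:** report the difference in response using all 78 subjects, with a 95% CI that reflects sampling error in both cohorts. Do not use a fixed 70% as a pass or fail line.
5. **2.5.7 and 2.10:** reconcile the direction of the p = 0.02 contrast before calling either regimen the stronger reference.

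The cost is some wording and one more historical comparison, with no extra patients. That comparison carries the usual historical-control bias and will be imprecise if the score-restricted cohorts are small. The conclusion may also turn out less favourable to alemtuzumab.

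### Section 8.3 has no rule for closing accrual once non-responders have already fixed the two-stage decision; adding one is a cheap improvement to a valid design

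*Combined protocol and SAP*

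**What the plan says.** Section 8.3 opens with its aim: "we would like to reject the treatment as quickly as possible with a small number of subjects if the treatment is not effective". It sets the null rate ("A response probability of 30% or less would warrant terminating the treatment on this subject population") and the target ("we hypothesize that the actual response probability using this treatment would reach 50% or more"), tested "at 0.05 significance level and 0.80 of the power". It chooses Simon's minimax design over the optimal one for its smaller maximum, 39 against 46: "This design is selected because it requires a smaller total number of subjects".

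The rule is applied at fixed sizes. "At the first stage, 19 subjects will be accrued and the null hypothesis will be accepted (i.e., the treatment will be terminated") with 6 or fewer responders at 3 months. With 7 or more, 20 further subjects are accrued, and H0 is accepted if 16 or fewer of the 39 respond. Section 8.3 then plans another 39 subjects for secondary comparisons, 78 in all, without saying whether they depend on the result in the first 39.

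Elsewhere, the formal stopping rule in section 8.5 covers treatment-related severe adverse events only. Under section 9.1 the investigator monitors efficacy, and the DSMB, reviewing every 6 to 12 months, can advise ending the trial early on safety or efficacy grounds. No numerical efficacy criterion goes with this.

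**The concern.** The stated aim is speed and few subjects if the drug does not work, but the rule as written waits for the full stage. After 13 non-responders in stage 1, seven responders of 19 are impossible. After 23 overall, 17 of 39 are impossible. Subjects enrolled from then on cannot change the primary decision. They would still receive a drug that the protocol describes as producing profound and lasting lymphopenia (section 2.7), with warnings of fatal infections and cytopenias (section 10.3.1). At stake is a small number of avoidable exposures in a trial that has already failed its own test.

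**Working it through.** **1. Reproduce the plan's design.** Inputs from section 8.3: p0 = 0.30, p1 = 0.50, limits 6/19 and 16/39. X1 is the number of responders among the first 19 and X2 the number among the next 20.

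- Probability of stopping at stage 1 when p = 0.30: P(X1 ≤ 6) = 0.6655.
- Probability of rejecting H0: sum over x = 7 to 19 of P(X1 = x) × P(X2 ≥ 17 − x). This gives 0.0455 at p = 0.30 and 0.8036 at p = 0.50.
- Expected enrolment at p = 0.30: 19 + 20 × (1 − 0.6655) = 25.69.

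A full search finds 39 to be the smallest total that meets 0.05 and 0.80. The design with the lowest expected enrolment at p = 0.30 is 5/15 and 18/46 (expected 23.63), so the quoted 46 reproduces too.

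**2. When the decision is fixed.** Stage 1: 19 − 6 = 13 non-responders. Overall: 39 − 16 = 23. The earliest possible stops are after 13 subjects in stage 1 and after 7 + 23 = 30 in stage 2. Stopping there changes no accept or reject decision, so alpha and power stay at 0.0455 and 0.8036.

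**3. How often stage 1 is decided early.** The failure is fixed before the 19th subject if at most 5 of the first 18 respond. That probability is 0.994, 0.867 and 0.534 at p = 0.10, 0.20 and 0.30.

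**4. Largest possible saving** (outcomes known at once; exact subject-by-subject recursion):

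| True response | Expected N, as written | Expected N, curtailed | Saving |
|---|---|---|---|
| 10% | 19.03 | 14.46 | 4.6 |
| 20% | 20.35 | 17.09 | 3.3 |
| 30% | 25.69 | 23.23 | 2.5 |
| 50% | 37.33 | 37.05 | 0.3 |

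**5. Allow for the endpoint delay.** Section 8.1 measures response at 3 months with confirmation at least one week later, taken here as 3.25 months. Accrual continues during that delay. The accrual rate is an assumption. One rough basis is 108 patients in the 1998 to 2003 protocols (section 2.5.7), which is 108/72 = 1.5 a month. Multiplying by the 11 of 26 with a high or intermediate score in Table 2 of section 2.2 gives 0.63 a month. The simulation uses random arrivals and assumes that accrual pauses after subject 19 until stage 1 is read.

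| Accrual per month | Saving at 10% | Saving at 20% | Saving at 30% |
|---|---|---|---|
| 0.5 | 3.0 | 1.9 | 1.4 |
| 0.63 | 2.6 | 1.6 | 1.1 to 1.2 |
| 1.5 | 0.9 | 0.5 | 0.3 |
| 2 | 0.4 | 0.2 | 0.2 |

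If six subjects always enter during the delay, the stage 1 saving is exactly zero, because 13 + 6 = 19.

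**6. Cost to the estimate.** At p = 0.30 the mean sample proportion at the end of the two-stage test is 0.280 as written. With curtailment it is 0.276 if two subjects enter during the delay and 0.271 if none do.

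**The case against.** An uncurtailed Simon design is standard. Each stage is defined to be read at its planned size, and the early look at 19 already serves the stated aim, stopping two thirds of trials at p = 0.30. This stands. A reader might infer that 8.3 contradicts itself or that its error rates are wrong. The documents do not support that: the figures reproduce, and the aim does not promise subject-by-subject stopping.

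A reader might also infer that the plan has no way to stop a visibly failing trial before 19 or 39. That goes too far. Section 9.1 gives the investigator efficacy monitoring and the DSMB a route to early termination. But this is discretionary, runs at 6 to 12 month intervals, and has no numerical criterion, so it does not replace a stated rule.

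The gain is small, and the accrual basis is weak. It comes from other protocols, and the text beside Table 2 counts 7 of 8 high-score responders where the table has 8 of 9. Section 10.1 expects no recruitment difficulty, so faster accrual is possible. The 10% scenario is the most favourable to curtailment. Low-probability patients are excluded (4.2.12), and the benefit at the hypothesised 50% is at most 0.3 subjects. All of this stands and limits the size of the point.

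Part of the saving also depends on the further 39 subjects. At p = 0.30 with two subjects entering during the delay, about 0.6 of the 1.0 saved arises in stage 2, and it is lost if those 39 are enrolled whatever the test shows. A reader might infer that they would be enrolled after a failed test. Section 8.3 does not say so; it is silent.

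Finally, section 10.4 places the study in data analysis only from January 27, 2017. A change now would spare no subject in this trial, so the point concerns the design as planned.

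**Conclusion.** The point holds as an optional improvement. Section 8.3 states an aim of few subjects if the drug is ineffective, but gives no rule for closing accrual once the 13th or 23rd non-responder has settled the matter. Curtailing for futility would keep both limits, alpha and power, and would save on average between almost nothing and about 4.6 subjects. At a true rate of 30% the figure is about 1 subject at 0.63 a month. Only the upper bound follows from the documents alone. The other savings rest on the assumed accrual rates, random arrivals, a 3.25-month delay and a pause between stages. The design remains a valid Simon minimax design.

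**What to change.** Keep 6/19 and 16/39 and add one sentence to section 8.3:

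> Accrual stops and H0 is accepted as soon as 13 of the first 19 subjects, or 23 of the first 39, are confirmed non-responders at 3 months; subjects already enrolled are followed and reported, and the additional 39 subjects are enrolled only if H0 is rejected.

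If the further 39 are not meant to depend on this test, replace the last clause with an explicit statement to that effect.

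The running cost is a tally of confirmed non-responders, from efficacy data that the investigator already monitors. The statistical cost is that a failed trial estimates the response rate from slightly fewer subjects and with slightly more downward bias. Section 8.4 should therefore say that the reported confidence interval takes account of the stopping rule.

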3.0 STUDY DESIGN

We propose a non randomized, off label, Phase I/II study of Alemtuzumab (Campath®) in MDS subjects who are likely to respond to immunosuppression based in our previous model (see section 2.2 prognostic indicators)

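### Do the 39 extra subjects in section 8.3 need a hypothesis and power, and is it unclear whether response is tested on 39 or 78?

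*Combined protocol and SAP*

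**What the plan says.** Section 8.3 tests a response probability of at most 30% against at least 50%, at the 0.05 level with 0.80 power, by a Simon minimax design. Nineteen subjects enter first, and "the null hypothesis will be accepted (i.e., the treatment will be terminated) if 6 or less subjects respond to the treatment at 3 months". Otherwise 20 more are enrolled, for a total of 39, and the null hypothesis "will be accepted if the total number of complete and partial responders at 3 months is 16 or less". One further sentence doubles enrolment: "An additional 39 subjects will be enrolled to allow for statistically valid subgroup comparisons of secondary endpoints such as response to cyclosporine", meaning subjects who relapse within six months.

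Section 8.2.6 says that relapsing responders "will be given CsA to determine if CsA will be beneficial under these circumstances" and that "The number of subjects who will receive CsA cannot be predicted since it will depend on the initial response to Campath which is unknown". Section 8.2 also says that response, its duration and the survival outcomes will be "compared within the FAB sub-groups and International Prognostic Scoring System categories of MDS". Section 2.10 puts the cyclosporine aim descriptively: "We will collect data on relapse rates and recovery of relapsing patients after institution of CsA". Section 8.4 plans binomial estimates, intervals and tests for response without naming a denominator. The safety simulation in section 8.5 runs to 78 subjects.

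**The concern.** Three things look wrong on a first reading.

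- **Unsupported size.** The first 39 subjects are derived from stated error rates. The second 39 rest on one sentence with no hypothesis, effect size, subgroup size or power, and its one example is a group whose size section 8.2.6 calls unpredictable.
- **No control for cyclosporine.** Section 8.2.6 wants to learn whether cyclosporine helps. Section 3.0 describes the study thus: "We propose a non randomized, off label, Phase I/II study". Section 5.2.2 gives cyclosporine to relapsing responders unless it is contraindicated, so no concurrent comparison is planned.
- **Two possible denominators.** With 39 in section 8.3, 78 in section 8.5 and neither in section 8.4, a reported response test might be the designed one or a different one.

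At stake would be an overconfident reading of small subgroup results, and a primary conclusion that depends on which set the analyst picks.

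**Working it through.** **1. The plan's own figure.** Inputs from section 8.3: 19 subjects in stage 1, continue at 7 or more responders; 20 in stage 2, reject at 17 or more of 39. With X1 ~ Bin(19, p) and X2 ~ Bin(20, p),

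P(reject) = Σ over x = 7 to 19 of P(X1 = x) · P(X2 ≥ 17 − x).

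This gives 0.0455 at p = 0.30 and 0.8036 at p = 0.50. A full search also returns this design as the minimax one. The primary design is sound.

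**2. What a test at 78 would do.** The plan gives none. The smallest cutoff with one-sided P ≤ 0.05 at p = 0.30 is 31, since P(X ≥ 31) = 0.0422 and P(X ≥ 30) = 0.0681 for Bin(78, 0.30). The two bars are 17/39 = 43.6% and 31/78 = 39.7%. Exact joint probabilities, with the stage 1 rule kept:

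| True p | Reject at 39, not at 78 | Reject at 78, not at 39 | Total |
|---|---|---|---|
| 0.30 | 2.9% | 1.5% | 4.4% |
| 0.40 | 4.7% | 15.2% | 20.0% |
| 0.50 | 0.4% | 10.1% | 10.5% |

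The third column needs trials that fail 17 of 39 to carry on to 78. Section 8.3 equates accepting the null in stage 1 with ending the treatment, and says a rate of 30% or less would warrant ending it. On that reading only the second column applies. A single test at 78 after stage 1 has type I error 3.2%, below 0.05. Claiming success on whichever test succeeds gives 6.1% if every trial passing stage 1 reaches 78. If only trials meeting 17 of 39 expand, success on either test is the same event as the designed rejection, so the error stays at 0.0455.

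**3. Numbers on cyclosporine.** Expected count = 78 × response rate × relapse rate among responders. The documents give neither rate for alemtuzumab in MDS, so both are assumed. The upper response value of 70% follows section 2.4.1, which reports over 70% with ATG-based treatment in the better-prognosis groups; section 4.2.12 excludes low predicted responders.

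- Low: 78 × 0.30 × 0.20 = 4.7
- Middle: 78 × 0.50 × 0.50 = 19.5
- High: 78 × 0.70 × 0.50 = 27.3

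With 39 subjects the middle case is 39 × 0.50 × 0.50 = 9.8. Exact 95% intervals for an observed 50% are 18.7-81.3% with 5 of 10 and 27.2-72.8% with 10 of 20. Doubling enrolment therefore narrows the interval from about 63 to about 46 percentage points in that case. The extra subjects buy precision, though the result stays wide.

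**4. Subgroup comparisons.** For an illustrative 30% v 50% contrast, which the plan does not state for subgroups, a 39 v 39 split has 35% power by two-sided Fisher test and about 44% by a pooled z test. Reaching 80% needs about 102 or 93 per group respectively. Power is low, but an exact test holds its level at any group size, and the plan states no power for these comparisons that it then misses.

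**The case for a change.** The strongest case for a change is that a doubling of enrolment should have a derived size, that the word valid promises more than an uncontrolled cyclosporine series can deliver, and that a manuscript is still to be written (section 10.6). The cautions in sections 8.2.2 and 8.2.4 cover only responder v non-responder comparisons. The denominator can matter: at a true rate of 40% the two tests would disagree in one trial in five if every trial passing stage 1 went on to 78.

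Part of this stands. The second 39 is not derived from the cyclosporine aim, the phrase is too strong, and section 8.4 does leave open the denominator for response estimates and intervals.

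The rest is weaker. The one-in-five figure needs both a continuation that section 8.3 speaks against and a test that appears nowhere in the plan. The missing control matters only if the aim is a causal claim. Comparing cyclosporine response between subgroups needs none, section 2.10 describes data collection, and section 8.2.6 openly states that the numbers are unpredictable. The subgroup power figures borrow the single-arm null and alternative as a contrast, and they do not address response duration or survival, which section 8.2 also compares.

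**Conclusion.** No change follows. The primary response test is fully specified in section 8.3 and reproduces exactly; it is made once, on 39 subjects. The missing denominator in section 8.4 is a gap that an analyst fills sensibly: apply the designed rule to the first 39 and give the number of subjects beside every estimate. Using all 78 for estimation is reasonable, and less affected by selection. Among trials that met 17 of 39, the mean observed rate at a true 30%, 40% and 50% is 46%, 48% and 53% in the first 39, but 38%, 44% and 51% in all 78.

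The rationale for the extra subjects is loosely worded, but it supports secondary aims in a non-randomized pilot, where unpowered subgroup summaries are usual. Their imprecision will be visible in the reported intervals: about 5 to 27 subjects on cyclosporine under the assumed rates, with an exact interval of 27-73% for an observed 50% of 20. Section 10.4 states that only data analysis remains after January 27, 2017, so revising a reason for enrolment cannot alter who was enrolled, any decision rule, or any estimate.

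This conclusion rests on reading acceptance of the null at 39 as ending treatment, as section 8.3 says for stage 1. If that reading were wrong, a test at 78 could differ from the designed one more often (4.4%, 20.0% and 10.5% of trials), but the plan would still contain only the test at 39.
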